| 11.3. Appendix 3. Kansas City Cardiomyopathy Questionnaire – 12 | 57 |
| 11.4. Appendix 4: Composite Congestion Score | 59 |
| 11.5. Appendix 5: Current Dyspnea Status - 5-Point Likert Scale | 60 |
| 11.6. Appendix 6: Dyspnea Status - 7-Point Likert Scale | 61 |
| 11.7 Appendix 7: Instructions for study staff administering Current Dyspnea Status Questionnaire (5-Point Likert Scale) and Dyspnea Status Questionnaire (7-Point Likert Scale)..... | 62 |

ABBREVIATIONS

| | |
|--------|---|
| AE | Adverse Event |
| AESI | Adverse Event of Special Interest |
| βhCG | Beta-human Chorionic Gonadotropin |
| BMI | Body Mass Index |
| Bpm | Beats per minute |
| CFR | Code of Federal Regulations |
| CRF | Case Report Form |
| CCS | Composite Congestion Score |
| CV | Cardiovascular |
| ED | Emergency Department |
| FDA | Food and Drug Administration |
| GCP | Good Clinical Practice |
| HF | Heart Failure |
| ICH | International Conference on Harmonization |
| IFU | Instructions for Use |
| IND | Investigational New Drug |
| IP | Investigational Product |
| IRB/EC | Institutional Review Board/Ethics Committee |
| ITT | Intent-to-Treat population |
| IV | Intravenous |
| KCCQ | Kansas City Cardiomyopathy Questionnaire |
| mmHg | millimeters of mercury |
| NYHA | New York Heart Association |
| PP | Per-Protocol population |
| ReDS | Remote Dielectric Sensing |
| SAE | Serious Adverse Event |
| SAP | Statistical Analysis Plan |
| 6MWT | Six Minute Walking Test |

1. INTRODUCTION

Heart Failure affects 6.5 million adults in the United States, a figure that is expected to grow to 8 million by 2030. Heart Failure is one of the most common causes of hospital admissions in patients over 65 with at least 1-2 million hospitalizations in the United States annually (Benjamin et al. 2018; Agarwal et al. 2016). Increasing signs and symptoms of congestion and fluid overload are the main reasons heart failure patients seek medical care and are hospitalized (Mullens et al., 2019). Symptoms of congestion generally worsen over several days or weeks providing a window of opportunity to intervene to avoid a potential unnecessary hospitalization (Schiff et al. 2003; Greene et al. 2018).

It is known that during periods of worsening congestion in heart failure, the bioavailability of oral furosemide is reduced and becomes highly variable (Vasko et al. 1985; Ellison et al. 2017). To overcome the limitation of oral furosemide in this setting, two strategies are typically employed. First, the oral furosemide dose is typically doubled, or additional oral diuretics (thiazide diuretics) are added to overcome the blunted pharmacological response to these agents. When this fails, clinicians often rely on giving IV diuretics, either in the hospital, an outpatient heart failure clinic or an infusion center, if available (Greene et al. 2018; Mullens et al. 2019). Hospitalization solely for the purpose of administration of intravenous furosemide is not a cost-effective strategy, is inconvenient for patients and their family, and places patients at risk for increased nosocomial infections and iatrogenic complications.

After hospitalization for heart failure, 25-30% of patients are readmitted within 30 days. It has been estimated that up to 50% of patients hospitalized for an episode of acute decompensated heart failure are discharged on oral diuretics with persistent signs and symptoms of congestion (Costanzo et al. 2007; Fonarow et al. 2005; Neuenschwander et al. 2007). The presence of congestion at discharge has been associated with an increased risk of 30-day all-cause mortality and rehospitalization for heart failure (Ambrosy et al. 2013). Patients hospitalized for heart failure should have a post discharge follow up visit within 14 days of hospital discharge (Yancy et al. 2013).

Alternative treatment paradigms that shift the management of congestion in patients with heart failure to outside of the acute care setting and improve congestion management post hospital discharge are urgently needed. If such options were available, another potential benefit would be early effective treatment in the outpatient setting to avoid early decompensation worsening into the full-blown syndrome of acute decompensated heart failure and potentially reduce 30-day readmission rates.

Furoscix is a novel formulation of furosemide buffered to a neutral pH to enable subcutaneous administration. It is intended to be administered subcutaneously via an On-Body Infusor, a compact, wearable, pre-programmed subcutaneous drug delivery system. The pharmacokinetics of Furoscix 80 mg administered subcutaneously over 5 hours in a biphasic regimen (30 mg in the first hour, followed by 12.5 mg/hour for the subsequent 4 hours) demonstrated comparable drug exposures to 2 doses of furosemide 40mg administered intravenously over 2 minutes 2 hours apart. In addition, the average 8- and 24-hour urine output and natriuresis was comparable between IV furosemide and Furoscix (Sica et al. 2018).

1.1. Rationale for the Current Study

The purpose of this study is to evaluate the effectiveness and safety of the Furoscix Infusor vs continued medical therapy in patients with chronic heart failure and fluid overload requiring augmentation in diuretic therapy outside of acute care setting.

The study is being executed under IND 118919 following all regulations required for Investigational Drug products.

1.2. Risk: Benefit Evaluation

1.2.1. Potential Benefits of Participating in the Study

There are no potential benefits to the participants beyond their contribution to the development and testing of this product.

1.2.2. Potential Risks of Participating in the Study

Furosemide has been widely studied and used clinically for over 50 years. It is generally considered a safe and effective pharmaceutical product. Patients may experience marked diuresis following the placement and activation of this drug-device combination product. Access to bathroom facilities is of critical importance and patients should be instructed to have instant access to suitable facilities. Marked diuresis may be accompanied by a drop-in blood pressure including orthostatic hypotension and associated signs and symptoms.

1.2.3. Risk Management

Subjects will be trained by the study staff on appropriate use of the Furoscix Infusor and will receive specific instructions and study materials created for the study (based on the Furoscix Infusor Instructions for Use) that include information regarding what to do in case of certain events during the drug delivery period.

Subjects should be transitioned back to their oral maintenance diuretic regimen when clinically indicated at the discretion of the investigator. After Subjects have been transitioned to their oral maintenance diuretic regimen, additional doses of Furoscix may be prescribed during the 30-day study period as needed based on the presence of symptoms of congestion (dyspnea, edema, and/or excess weight gain) as determined by the investigator. No more than 7 doses of Furoscix is permitted during the 30-day study period. Additional doses beyond 7 requires approval by the medical monitor. If modifications are made diuretic regimen after Subjects' are transitioned to their oral maintenance diuretic regimen, including additional doses of Furoscix for the treatment group or oral diuretics for the treatment as usual control group, the Subjects' follow-up assessments and timing of those assessments will be based on the investigator's clinical judgement.

Subjects will receive scheduled at-home telephone calls from a HF nurse, or designee, on Days 2, 4, 5, 6 and 17. Four planned in-clinic visits will be conducted: the first occurring on Day 1, the second on Day 3, the third occurring on Day 7 and the fourth occurring on Day 30 \pm 5 days. Unscheduled calls and clinic visits can be conducted as needed. The primary purpose of the calls will be to evaluate the clinical response to diuretic therapy and the need to adjust diuretic therapy. Clinic visits will include assessment of creatinine and electrolytes.

2. STUDY OBJECTIVES

The objectives of this study are:

Primary Objective:

- To provide pilot data on the effectiveness and safety to inform a pivotal trial

Secondary Objectives:

- To inform population enrichment strategies
- To refine pivotal trial endpoints and analytical methods
- To identify operational challenges of study design
- To assess patient adherence, competence, and experience
- To familiarize staff and patients with device application and use

3. INVESTIGATIONAL PLAN

3.1. Overall Study Design and Plan

This study is a multicenter, randomized, open label, controlled study evaluating the effectiveness, and safety of the Furoscix Infusor vs continued medical therapy in patients with chronic heart failure and fluid overload requiring augmentation in diuretic therapy outside of acute care setting. The study will enroll 51 subjects 18 years or older with chronic heart failure, NYHA Class II-IV symptoms, evidence of fluid overload requiring additional diuresis as assessed by the investigator, with either reduced or preserved LVEF, who are on background therapy including oral furosemide equivalent dose between 40 and 160 mg of loop diuretic daily, inclusive or equivalent (20-80 mg per day of torsemide or 1-4 mg per day of bumetanide). The subjects will be randomly assigned (2:1) to receive Furoscix Infusor vs continued medical therapy.

Each Subject will complete Screening, Treatment, and Follow-Up Phases on an outpatient basis. During the Screening Phase, all subjects who sign the informed consent form and satisfy the inclusion/exclusion criteria will be enrolled into the trial. Drug administration will start on the day of enrollment (same day as screening after all eligibility criteria have been satisfied) and subject has been randomized. NT-proBNP will be sent to centralized laboratory for subjects who qualify to participate.

The Treatment Phase will start once screening procedures have been completed and eligibility is confirmed. Subjects and/or their caregivers will be trained on device preparation, placement and removal in accordance with product instructions of use (IFU). Furoscix will be administered daily via the Furoscix Infusor whereby 80 mg is administered subcutaneously over 5 hours in a biphasic regimen (30 mg in the first hour, followed 12.5 mg per hour for the subsequent 4 hours). Within a single 24-hour period, the 80 mg dose can be repeated at the discretion of the investigator \geq 2 hours after the completion of the first dose. The dosing frequency and duration of therapy will be determined by the investigator based on an estimated volume of diuresis desired to transition Subject back to their oral maintenance diuretic therapy. The decision of when to discontinue Furoscix and switch to oral diuretics will be based on clinical judgement.

Subjects will be followed up at an in-clinic visit on Days 1, 3 and 7 and through a phone call from site staff on Days 2, 4, 5, 6 and 17 to assess for signs and/or symptoms of congestion.

After the Day 7 clinic visit, subjects will continue to utilize the provided equipment and weigh themselves and record their blood pressure and heart rate approximately the same time each morning. Additional doses of Furoscix can be prescribed as needed due to congestion symptoms (e.g. dyspnea, edema, and/or excess weight gain) as determined by the investigator. In addition to the scheduled phone and clinic visits, the investigator can utilize unscheduled clinic or phone visits for additional assessments at any time. No more than 7 doses of Furoscix is permitted during the 30-day study period. Additional doses beyond 7 requires approval by the medical monitor. If diuretic modifications are made after Subjects' are transitioned to their oral maintenance diuretic regimen, including additional doses of Furoscix in the treatment group or oral diuretics for the treatment as usual control group, the Subjects' follow-up assessments and timing of those assessments will be based on the investigator's clinical judgement. Unscheduled clinic and phone visits can be conducted as needed. All follow-up assessments done by phone or in-clinic will be documented.

For the Follow-Up Phase, Subjects will return to the clinic on Day 30 \pm 5 days (30-days post randomization) for a final follow-up visit where effectiveness and safety assessments will be performed.

3.2. Furoscix Infusor

The Furoscix Infusor is a drug-device combination product consisting of Furoscix (Furosemide injection, 80 mg per 10 mL), a novel, pH neutral furosemide formulation optimized for subcutaneous administration and contained in a prefilled, Crystal Zenith (CZ) cartridge, and a proprietary wearable, pre-programmed on-body delivery system, the Infusor, based on the SmartDose Gen II 10 mL (West Pharmaceutical Services).

The Infusor is a compact, ethylene oxide (EtO) sterilized, single-use, electro-mechanical (battery powered, micro-processor controlled), on-body delivery system that administers a fixed dose of drug product from a prefilled cartridge assembly into subcutaneous tissue of the abdomen. It is intended for use by patients, caregivers, or a health care professional (HCP) at home or in a clinic setting.

The Furoscix Infusor is 117 mm x 62 mm x 30 mm (length x width x height) and weighs approximately 80 grams without the drug cartridge and 90 grams, with a filled drug cartridge inserted into the drug compartment. It has an integrated, adhesive patch which attaches the Infusor to the skin for dose administration. The device with adhesive is removed from the skin following completion of the dose and discarded.

The system delivery parameters will be pre-programmed as part of the manufacturing process to deliver 80 mg (10 mL) furosemide over 5 hours using a biphasic delivery profile of 30 mg furosemide (3.75 mL) over the first hour and 12.5 mg furosemide (1.56 mL) per hour over the subsequent 4 hours. The device elements are shown in [Figure 1](#).

[figure not shown]

Figure 1: Main components of Furoscix On-Body Infusor

The Furoscix Infusor utilizes a primary container, which consists of the CZ cartridge (CZ barrel and elastomeric septum) and elastomeric piston. The primary container assembly is prefilled with the Furoscix as part of the fill-finish process.

Following removal of the Furoscix Infusor from the packaging, the drug compartment of the device is opened by the user, which turns the device on, and a built-in self-test is performed to verify the needle/button position, correct software parameters, the device was not operated prior to the current activation and the motor and batteries are functional.

The user inserts the prefilled Cartridge into the drug compartment, closes the compartment, removes the adhesive liner and attaches the loaded Furoscix Infusor to the skin of the abdomen. Pressing the activation button automatically inserts the small, 27-gauge, 6 mm needle into the subcutaneous tissue and drug administration is initiated. The needle is protected within the device and can only be deployed when the prefilled Cartridge is in place, the cartridge compartment is closed, the device is adhered to the patient, the safety latch is closed, and the activation button has been pressed. Dose administration stops automatically upon completion of drug delivery or opening of the safety latch upon the removal of the device from the abdomen.

The Furoscix Infusor is designed to administer the entire dose without user intervention. The dose volume and dose administration time cannot be changed by the user. Both visual and auditory notifications provide feedback on the progress of drug administration. In the event of a drug delivery error, visual and auditory notification will alert the user. Once drug administration is complete, accompanied by visual and auditory notifications, the user removes the system with the administration needle by carefully peeling the adhesive from the skin which automatically opens the safety latch to conceal and protect the administration needle. The empty Cartridge cannot be removed from the system after administration of the

drug product and the integrated Cartridge/Infusor are disposed of together. The device is battery-powered and enables removal of the battery by the user prior to disposal.

The clinical study will include training the Subject and/or caregiver in the preparation, placement, activation and removal of the Furoscix Infusor based on the Furoscix Infusor Instructions for Use (IFU).

Training for study staff on the device operation and placement following the IFU and subject specific instructions will be conducted during an Investigator Meeting(s) and/or at the Site Initiation(s).

Subjects will be instructed on the use of the Furoscix Infusor by the investigator and/or study staff in accordance with the IFU and subject specific instructions. The initial dose of the study product may be administered in the clinic or at home on the day of enrollment. Additional doses will be provided to the subject for self-administration or administration by a caregiver in the home setting as directed by the investigator or study staff.

Study Subjects will be provided with instructions based on the IFU of the product. These include to not shower, bathe, swim or do activities that may cause sweat while wearing the Furoscix Infusor because it contains parts that should not get wet. Participants will be informed that marked diuresis may ensue after activation and that they should have access to bathroom facilities for up to 8 hours after starting the infusion.

If the Subject experiences leakage or pain during the infusion period, they are instructed to call the study team at the clinical site as designated on the informed consent form and subject specific instructions. If the infusion is interrupted for any reason (i.e. see visual and hear audio notifications) or the device becomes detached during the infusion period, subjects are instructed to call the study team at the clinical site. Following dosing and device removal, subjects should place the used Furoscix Infusor in the box and bring back to the clinic at their next scheduled study visit. Subjects will return all Furoscix Infusors by the Day 30 in-clinic visit.

3.2.1. Primary Endpoints

- Improvement in a composite/combined morbidity/mortality endpoint at 30 days using the Finkelstein Schoenfeld method.
 - CV death
 - HF hospitalization
 - Urgent ED/Clinic visit for worsening heart failure (defined as IV diuretics, augmentation of or new administration of metolazone)
 - Change in NT-proBNP from baseline at Day 7
- Incidence of Adverse Events, Adverse Events of Special Interest, and Serious Adverse Events

3.2.2. Secondary Endpoints (through 30 days)

- Days alive and HF event free days
- Global Visual Analog Scale

- Composite Congestion Score
- 5-point Current Dyspnea Score
- 7-point Dyspnea Score
- Health-related quality of life (KCCQ-12)
- Renal Function and Electrolytes
- Weight
- Exercise tolerance (6MWT)
- % Lung Fluid Measurement via Remote Dielectric Sensing (ReDS)

3.2.3. Adverse Events of Special Interest over 30 Days

- Worsening kidney function, defined as increase of ≥ 0.5 mg/dl in serum creatinine
- Hyperkalemia, defined as $K > 5.5$ mEq/L
- Hypokalemia, defined as $K < 3.5$ mEq/L
- Hypomagnesemia, defined as $Mg < 1.5$ mg/dL

4. SELECTION OF STUDY POPULATION

4.1. Inclusion Criteria

Female and male Subjects are eligible for inclusion only if all the following criteria are met:

1. Age 18 years or older.
2. Diagnosis of symptomatic chronic heart failure (NYHA Class II-IV) with background loop diuretic therapy for at least 4 weeks.
3. Need for augmented diuresis outside of the acute care setting as determined by the investigator.
4. On background therapy including daily total furosemide equivalent dose (40-160 mg) of loop diuretic or equivalent.
5. The subject must have signs of volume expansion, defined as two or more of the following six signs:
 - a) jugular venous distention
 - b) edema ($\geq 1+$)
 - c) ascites
 - d) pulmonary congestion on chest x-ray
 - e) pulmonary rales
 - f) NT-proBNP ≥ 1000 pg/ml (1400 for patients in atrial fibrillation) or, for patients not on Entresto, BNP ≥ 200 (400 for patients in atrial fibrillation)
6. Increase over the preceding 30 days in at least one of the following symptoms characteristic of worsening heart failure:
 - a) dyspnea
 - b) fatigue
 - c) exercise intolerance
7. Adequate environment for at home administration of Euroscix by patient or caregiver.

4.2. Exclusion Criteria

A Subject is not eligible for inclusion if any of the following criteria apply:

1. Suspected high risk clinical instability with outpatient treatment.
2. Presence of a complicating condition, other than heart failure likely to require

hospitalization in next 30 days.

3. Pregnant women or women of childbearing age who are not willing to use an adequate form of contraception.
4. Known allergy to the active and inactive ingredients of the study medication or device adhesive.
5. On experimental medication or currently participating in another interventional research study.
6. eGFR ≤ 20
7. Serum potassium at baseline > 5.4 or < 3.6
8. Concomitant infection
9. Heart rate > 110
10. Received IV furosemide or IV bumetanide within last 24 hours

4.3. Removal of Subjects from Therapy/Premature Discontinuation

Subjects may voluntarily withdraw at any time, but once treatment has occurred, every attempt will be made to continue assessments to ensure the safety of the subject. A Subject will be discontinued from the study for the following medical or administrative reasons:

- Subject wishes to withdraw consent
- Safety reasons, e.g. AEs
- Subject non-compliance with study procedures required by the protocol
- Principal Investigator discretion

The Investigator may discontinue individual Subjects from the study if anatomical or skin conditions prevent proper placement of the device.

Subjects who withdraw or are withdrawn prior to study completion may be replaced. As far as possible, subjects who withdraw from the study after treatment, and before completion should be seen by the PI or delegate and undergo the assessments and procedures scheduled for the follow-up visit.

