6.2.2. Treatment Phase (Day 0)

After the screening activities have been completed and laboratory analyses reviewed to confirm eligibility, the patient may be randomized (2:1) to receive either Furoscix or continued medical therapy with oral diuretics. Subjects randomized to continued medical therapy will follow the same schedule of assessments, excluding study product administration.

The initial dose of the study product should be administered after randomization. If randomized to Furoscix, product training with subject and/or caregiver will be conducted. The initial dose of the study product may be administered in the clinic or at home on the day of enrollment. Study staff will dispense additional doses of Furoscix. Subjects will be provided a Subject Diary in which to record any observed device issues and self-assessments that will be completed at home.

The Subject will be reminded to use the provided equipment to weigh themselves and record their blood pressure and heart rate and complete the patient global assessment VAS upon returning home and first thing in the morning on Day 1. They will also be reminded to bring their study product (device) and Subject Diary back to the clinic on Day 1.

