6.2.14. Physical Examinations

A limited physical examination will be performed consisting of assessments of the following: skin of abdominal area, lungs/chest, heart, abdomen and periphery.

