## 14. ANALYSIS POPULATIONS

**Intent-to-Treat (ITT):** ITT population will include all randomized subjects. The subjects in ITT population will be analyzed according to the treatment group they were originally randomized.

**Safety:** Safety population will include all randomized subjects who received at least one dose of Investigational Product (IP). The subjects in the Safety population will be analyzed and presented according to the actual treatment received.

**Per-Protocol (PP):** All randomized subjects who received at least one dose of the IP, completed the 30 Day clinic visit assessments and have a Day 7 NT-proBNP value available for analysis.

All effectiveness analyses, including the primary endpoint and baseline characteristics will be performed on the ITT and Per-Protocol populations. Safety analyses will be performed on the safety population.

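### Protocol Section 4.3 takes subjects out of the study rather than off therapy, by one route open only to the Furoscix arm, and does not secure their 30-day outcomes

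*Protocol*

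**What the plan says.** Protocol Section 4.3 lists consent withdrawal, safety, non-compliance and investigator discretion as reasons for which a subject will be discontinued from the study. It then adds a permissive ground: "The Investigator may discontinue individual Subjects from the study if anatomical or skin conditions prevent proper placement of the device".

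Two sentences in 4.3 deal with follow-up of leavers. The first says that "once treatment has occurred, every attempt will be made to continue assessments to ensure the safety of the subject". The second says that, as far as possible, "subjects who withdraw from the study after treatment, and before completion should be seen by the PI or delegate" and have the follow-up-visit assessments. On replacement: "Subjects who withdraw or are withdrawn prior to study completion may be replaced". No limit, arm or allocation method is given.

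The order of events is in Protocol 6.2.2. After randomization, "If randomized to Furoscix, product training with subject and/or caregiver will be conducted", whereas "Subjects randomized to continued medical therapy will follow the same schedule of assessments, excluding study product administration". The only device-related exclusion in 4.2 is allergy, including to the adhesive; skin and anatomy are not mentioned. Yet the limited physical examination at screening already covers "skin of abdominal area, lungs/chest, heart, abdomen and periphery" (6.2.1 and 6.2.14).

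On analysis, SAP Section 14 states that "ITT population will include all randomized subjects", analyzed as randomized. SAP Section 15 imputes nothing on endpoints. The pairwise algorithm in SAP 15.2.1 scores death, HF hospitalization and urgent visits as happened or not by 30 days, with no entry for unknown. The Protocol synopsis (Study Assessments and Procedures) says survival and unplanned HF events are assessed for 30 ± 5 days after enrollment. It does not say whether this continues after discontinuation.

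**The concern.** Stopping a product and leaving a trial are different events, and 4.3 treats them as one. Nothing in it lets a subject stop the product and remain under observation for the endpoint.

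That would matter less if the exits were the same in both arms. The placement ground is not: a control has no device to place. In an open-label trial it can act once the allocation is known. A Furoscix subject removed on this ground before a first infusion may never have had treatment in the sense of the follow-up sentences, so neither sentence clearly applies. Even where they do apply, they promise continued assessment for safety and one exit visit, not ascertainment of events to Day 30.

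At stake is the primary composite, which needs 30-day event status for every randomized subject. If status is missing more often in one arm, and for reasons linked to prognosis, the comparison is no longer fully randomized. Outcomes never collected cannot be restored by analysis. The Per-Protocol set does not help, because it requires the Day 30 visit and a Day 7 NT-proBNP value and so drops most such leavers.

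**Working it through.** **Plan's own figure.** SAP Sections 2 and 4 give 51 subjects randomized 2:1. 51 × 2/3 = 34 and 51 × 1/3 = 17, as stated. There is no power, effect-size or dropout figure to reproduce.

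**Weight of one subject.** 1/34 = 2.9% of the Furoscix arm. There are 34 × 17 = 578 cross-arm pairs, and each Furoscix subject is in 17 of them (17/578 = 2.9%). Three leavers would be 3/34 = 8.8%; five would be 14.7%. Replacing one to seven leavers one for one gives 52 to 58 randomized against the planned 51.

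**The scoring of leavers decides the effect.** Assume a true 30-day event proportion of 20% in the Furoscix arm and three leavers with the same risk and no later data. Observed events are 0.20 × 31 = 6.2.
- Leavers kept in the denominator as event-free: 6.2/34 = 18.2%.
- Denominator of subjects present at the visit, the general percentage convention in SAP 7.1: 6.2/31 = 20%.

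The SAP does not say which applies to 30-day events.

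**Finkelstein-Schoenfeld illustration.** This is a simulation under no treatment effect, with 34 and 17 subjects, 6,000 trials per setting and the SAP's statistic. The tiers were HF hospitalization, urgent visit and NT-proBNP change; the death tier was omitted. Every rate is an assumption: hospitalization 10% or 25%, urgent visit 10%. Placement problems are equally common in both arms, but lead to removal only from Furoscix. Affected subjects have either the same prognosis or a worse one (event risk doubled, NT-proBNP change 0.5 SD worse). The win difference is the share of cross-arm pairs won by Furoscix minus the share lost. Ranges span the two hospitalization rates.

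| Handling of leavers | Prognosis | 10% removed: win difference; two-sided error | 20% removed: win difference; two-sided error |
|---|---|---|---|
| Replaced and left out of analysis | same | about 0; 4.5–4.6% | about 0; 4.1–4.9% |
| Replaced and left out of analysis | worse | +0.03 to +0.04; 5.1–5.5% | +0.06 to +0.08; 6.1–7.0% |
| Kept in ITT as event-free, NT-proBNP tied | same | +0.02 to +0.03; 5.2–5.9% | +0.04 to +0.07; 6.2–8.2% |
| Kept in ITT as event-free, NT-proBNP tied | worse | +0.05 to +0.07; 6.6–7.4% | +0.10 to +0.14; 10.6–15.0% |

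With everyone followed to Day 30, the win difference is about 0 and the error 4.4–5.6% across all removal rates from 0 to 20%. The nominal level is 5%, with Monte Carlo error of about ±0.6 points.

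The distortion runs from nil to substantial. What separates the rows is the scoring of leavers and the link to prognosis, and the documents settle neither.

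**The case against.** The strongest case against is that the documents point less firmly to lost data than 4.3 does when read alone. Three stronger readings are tempting, and none is supported.

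*Controls never receive treatment, so a control who leaves has no follow-up.* Protocol 5.1 and the synopsis row on study treatments do describe only the study drug and device. But Section 3.1 puts every subject through a Treatment Phase and calls the control arm treatment as usual, and 6.2.2 places randomization under the Treatment Phase heading. The term is undefined and either reading is open. The firmer gap is the Furoscix subject who was never dosed.

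*Outcomes are lost selectively.* The synopsis sets event assessment from enrollment without regard to arm or dosing. The placement ground is permissive, the four listed grounds are not arm-specific, and abdominal skin is examined in everyone at screening. This is a risk, not a stated consequence.

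*Replacement biases the comparison.* It applies to both arms and removes no one from ITT. No rule says a replacement enters the leaver's arm. In the illustration replacement produces bias only when leavers are left out of the analysis and leaving is tied to prognosis.

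It is also fair that this is an exploratory pilot without a power calculation (SAP Section 4), and that a Day 0 check cannot find skin problems that develop later.

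What stands: no text says that event assessment continues after discontinuation, 4.3 ends participation for reasons that need only end therapy, and one of those reasons exists in a single arm.

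**Conclusion.** The point holds as a risk created by the wording. Section 4.3 merges stopping therapy with leaving the study and adds an exit that only the Furoscix arm can meet, possibly after open-label randomization. It does not secure 30-day event status for those who leave. The ITT definition, the absence of imputation and the missing score for unknown status mean the analysis cannot repair the loss.

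The size cannot be stated. The documents give neither a withdrawal nor a placement-failure rate, so the number affected could be zero. A fall in the Furoscix event proportion from 20% to about 18% with three leavers should not be read as the expected bias, because it rests on counting leavers as event-free, which the SAP does not say. The simulated error rates likewise hold only under their assumed rates, prognosis and scoring.

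The exploratory status lowers the consequence of a distorted p-value. It does not remove the reason to act: the stated objective is effectiveness and safety data to inform a pivotal trial, and with 34 and 17 subjects a few uncollected outcomes matter.

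**What to change.** In Protocol Section 4.3 and the related sections:

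(a) State that discontinuing study product or assigned therapy, for any reason, does not end study participation. All randomized subjects in both arms stay on the scheduled contacts to Day 30, covering vital status, HF events and the Day 7 NT-proBNP, unless they withdraw consent. Decisions to stop product remain with the investigator and are not changed.

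(b) Replace the two treatment-based triggers for follow-up of leavers with randomization, so that both arms and never-dosed subjects are covered.

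(c) Judge device-placement suitability for all candidates before randomization, at the Day 0 abdominal skin examination already scheduled, and reflect this in 4.2. Problems that develop later are handled by (a).

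(d) State that any replaced subject stays in ITT as randomized, or drop replacement.

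Some subjects may still withdraw consent, so the SAP should also say how unknown 30-day status is scored in 15.2.1.

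The cost is an amendment to wording. A few candidates would be screened out before randomization, and some subjects off product would still attend visits already in the schedule.
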